## Abstract

**Background** Transfer from paediatric to adult care for chronically ill adolescents is associated with no-shows and low treatment adherence, as well as anxiety and concerns among parents. Studies show that support for parents results in better transition for both adolescents and parents. The overall goal is to improve chronically ill adolescents' transition to adult care by preparing and supporting the parents. The study aim is to improve parents' (of chronically ill adolescents, 16-18 years) transition readiness by offering them a brief transition program.

**Method** The intervention will be evaluated in a randomised controlled trial (RCT) study over two years. The project will be carried out in four paediatric and adult outpatient clinics at Rigshospitalet, Copenhagen University Hospital, Denmark: nephrology, hepatology, neurology and rheumatology. The intervention consists of a brief transition program (ParTNer-STEPs) targeting parents of chronically ill adolescents aged 16,5 -18 years old. The program consists of three components: 1) a website with information about the adult department and legal changes as well as advice from other parents and young people, 2) online educational events (webinars) for parents and 3) transfer consultations across the paediatric and adult department. Based on a power calculation, we aim to include parents of minimum 62 adolescents. The trial is carried out in 2021-2023, with main measurements at pre-intervention baseline, at transfer, and three months follow-up (post-intervention). Primary outcome: Parents' transition readiness (TR). Secondary outcomes: Adolescents' TR, Allocation of responsibility, Uncertainty and quality of life.

**Discussion** The study will establish whether ParTNer-STEPs is effective in increasing parents' and adolescents' TR, reducing parental uncertainty, and facilitating a shift of treatment responsibility from the parents to the chronically ill adolescent.

### Trial registration

**Keywords** Adolescent, chronically ill, parents, transitional care and patient transfer.

## Background

Parents play an essential role during childhood. Especially in the case of chronic illness, parents have a great responsibility for their child's daily care and treatment. An important milestone in adolescence is gradual independence from parents, and in chronic illness, a gradual shift in treatment responsibilities from the parents to the adolescent is expected (Christie and Viner 2005, Williams, Mukhopadhyay et al. 2007, DiClemente 2009, Shaw, Heath et al. 2021).

Studies have found that parents of chronically ill adolescents form a particularly close bond with their child, and may fear handing over treatment responsibilities to the teenager (Akre and Suris 2014, Woodgate, Edwards et al. 2015, Thomsen, Khoury et al. 2019). This could delay individuation (Suris, Michaud et al. 2004). We have also found that parents were concerned and felt uncertain about their child's transition to adult care (Thomsen, Hanghøj et al. 2021).

The organisational differences in paediatric and adult care can make the transition difficult. Furthermore, the expectations of both the parents and the adolescent change profoundly with an increasing focus on the young patient's autonomy (van Staa, Jedeloo et al. 2011). Studies have found that a significant proportion of chronically ill adolescents develop complications and experience exacerbations of their disease during the transitional phase (Gore, Bloem et al. 2011). In the case of organ transplantation, adolescents have a significantly higher risk of graft failure compared to children and adults (Andreoni, Forbes et al. 2013, Foster, Dahhou et al. 2016). Studies have shown that the transition phase also affects the parents significantly, including an increased risk of developing anxiety and stress (Akeson, Worth et al. 2007, Fredericks, Dore-Stites et al. 2011, Rutishauser, Akre et al. 2011, Heath, Farre et al. 2017, Sarigol Ordin, Karayurt et al. 2017).

Studies have showed that appropriate parental support can increase adolescents' adherence to treatment (King, Berg et al. 2012, Reed-Knight, Blount et al. 2014), while both parents' difficulties in delegating treatment responsibility and lack of parental support constitute significant barriers to adolescents' treatment adherence (Hanghøj and Boisen 2014).

Lack of transitional care before transfer to adult care is associated with an increased number of no-shows at outpatient clinics. International studies have found that 25-50% of chronically ill adolescents do not attend their first consultation in adult care and there is a significant over-frequency of no-shows in the 17 to 40-year-old group (Downing, Gleeson et al. 2013, Eriksen and Kjellberg 2013, Gleeson, Davis et al. 2013).

In the last decade, there has been an increased focus on transition programmes targeting adolescents (Gabriel, McManus et al. 2017, Schmidt, Ilango et al. 2020). A systematic review from 2017, a cohort study from 2018, and several recommendations conclude that health care professionals (HCP) also should focus on supporting parents in their transition and providing the parents with both help and tools to support their child's transition (NICE 2016, Heath, Farre et al. 2017, Colver, McConachie et al. 2018, DanishHealthAuthority 2020). Our clinical experience has shown that adolescents' self-management skills are mainly developed at home, guided by their parents, rather than in consultations with health professionals. Even though a need for parental support during transition has been established, there have, to our knowledge, not been developed and evaluated any transition programs targeting parents.

Based on The UK Medical Research Council's (MRC) guidance on developing, evaluating and implementing complex interventions (Craig, Dieppe et al. 2019) we have developed and pilot tested a brief transition program

targeting parents, ParTNer-STEPs. The transition theory SMART guided the overall focus of the intervention. The program's feasibility and relevance were secured by inviting parents, adolescents and HCP in a cocreation process during each step in the development phase (A thorough description of the development phase will be published elsewhere).

## Material and method

### Aim and hypotheses

The overall goal of this study is to improve chronically ill adolescents' transition to adult care by preparing and supporting the parents.

We hypothesize that a nurse-led transfer intervention focusing on parents' knowledge, skills and attitudes will:

- 1) improve the parents' readiness for their child's transition to adult health care
- 2) support the parents' gradual handing over of treatment responsibility to the adolescent and, that an improvement in parental transition readiness will
- 3) strengthen the adolescent's self-management skills and increase his/her readiness for transition.

Thus, the study aim is to improve parents' (of chronically ill adolescents, 16-18 years) transition readiness by offering them a brief transition program.

### Design

The study design is a randomized controlled trial (RCT) study with one intervention arm (ParTNer-STEPs: Parents in Transition – a Nurse-led Support and Transfer Education Program + standard care) compared with a control arm (standard care).

### Setting

The intervention will be carried out at the nephrology, hepatology, neurology and rheumatology paediatric and adult outpatient clinics at Copenhagen University Hospital, Rigshospitalet, Denmark. We have chosen these four specialties, because low treatment adherence and non-attendance in the patient group could result in permanent disabilities or critical consequences. In Denmark, adolescents transfer to adult care when turning 18 years old regardless of the adolescent's maturity or transitional readiness. Each paediatric clinic has at least one youth ambassador (a nurse with special interest and training in adolescent medicine). The existing transitional care includes youth consultations using the split-visit model, where health care professionals (HCP) both spend time alone with the adolescent and with the adolescent and parents together (Borus and Woods 2016) with the THRxEADS anamnesis (Transition, Home, Medication and treatment, Education and Eating, Activities and affect, Drugs and Sexuality) (Chadi, Amaria et al. 2017) as the basis of the conversation as well as assessment of adolescent transition readiness. The clinics currently have no programmes targeting parents.

## Participants

### Eligibility criteria

Participants are parents, stepparents or guardians (will subsequently only be referred to as parents) of chronically ill adolescents affiliated with the four paediatric outpatient clinics. The adolescents will participate in

the intervention and contribute with outcome measurements. Parents who meet the following criteria will be invited to participate in the study. *Inclusion criteria:* Parents to chronically ill adolescents who 1) are aged 16.5-17.5 years (can be recruited up to six months before transfer), 2) have been diagnosed for minimum six months, 3) have regular check-ups at the Department of Paediatrics and Adolescent Medicine's nephrology, hepatological, neurological and rheumatological outpatient clinics at Rigshospitalet, Denmark, 4) will be transferred to an adult hospital department and 5) are mentally and cognitively able to take responsibility for their own treatment. *Exclusion Criteria:* 1) Parents who do not read and speak Danish and 2) Parents of adolescents who will be transferred to their family doctor at the age of 18 year.

### Recruitment

Potential participants will be contacted by the paediatric nurses at the four outpatient clinics and briefly informed of the study. If the parents are interested in the project, the project coordinator will provide the parents with oral and written information of the study, including the fact that they can withdraw from the study at any time without consequences for their child's treatment. There will also be provided written information to their adolescent child and the adolescent will also get the opportunity to speak directly to the project coordinator, if they have any questions. Finally, after time to consider their participation in the project, a written consent will be obtained. Under the recruitment process we will carefully consider the risk of coercion, autonomy, and confidentiality.

### Randomisation

[figure not shown]
Randomisation will be conducted after screening and written consent of parents. Randomisation will be conducted by computer-generated (REDCap) random numbers as a dyad (adolescent and parents) with a ratio of 1:1 (using algorithm to stratify by the four outpatient's clinic). The dyads will be randomised into two groups 1) receive the intervention (standard care plus ParTNer-STEPs until their child's transfer to adult care) or 2) standard care (control group). Once the database has defined a dyad's allocation, no changes can be made. Those randomised to the intervention arm will then receive access to the intervention materials.

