### Intervention

The intervention consists of a transfer program (ParTNer-STEPs), offered to the parents from 6 – 18 months before their adolescent child is transferred to adult care (depends on when the participant is recruited before transfer).

ParTNer-STEPs (Parents in Transition – a Nurse-led Support and Transfer Education Program) (figure 1) consist of

- 1) an informative website
- 2) online educational events for parents
- 3) transfer consultations across the paediatric and adult department.

**Figure 1:** Model of the intervention

**Informative website** available for parents from recruitment until follow-up. The website will focus on:

- dissemination of relevant knowledge regarding legal changes, education questions etc
- guidance and tools in relation to how the parents can prepare their adolescent child
- introduction to adult care incl. expectations alignment
- experiences from other parents and adolescents
- Q&A incl. parents' possibility to submit own questions

**Online educational events** offered twice a year as an online webinar with short presentations on different topics. The webinar will not be available for parents after their child has transferred to adult care. The educational events will be focused on:

- Emotions and thoughts during transition
- Adolescence, chronic illness and autonomy
- Knowledge sharing

**Transfer consultations** across the paediatric and adult department. The transition consultations consist of:

- a preparatory consultation (3-6 months before transfer) with the paediatric nurse where focus is on the adolescent's skills, expectations, goals and emotions).
- a farewell consultation with the paediatric nurse (0-3 months before transfer). Focus on relationships, expectations, goals
- a joint consultation (at transfer) where both the paediatrician and the adult physician will be present Focus on cooperation/partnership, relationships, knowledge
- a welcoming consultation with the nurse from the adult care (0-3 months after transfer) Focus on expectations, skills, relationships

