### Data collection and management

Data will be collected through questionnaires at baseline and every six months up to three months after the adolescent's transfer to adult care (Figure 2). Transfer time is registered as the date for the last consultation at paediatric. Questionnaires will be sent out via email or by post based on participants' wishes. The questionnaires will take approximate 10 minutes to complete. All data will be handled confidential and stored in the password protected software REDCap.

**Figure 2** Model of time frame

Questionnaires	Time frame				
	Baseline	6 months	12 months	Transfer	3 months follow-up
Socio-demographic					
Parents	X				
Transition readiness (TR)					
Parents	X	X	X	X	X
Adolescent	X	X	X	X	X
Allocation of Responsibility (AoR)					
Parents	X	X	X	X	X
Adolescent	X	X	X	X	X
The Uncertainty Scale					
Parents	X			X	
EQ-5D-5L					
Adolescent	X			X	X
Experiences of transfer					
Parents					X
Transfer satisfaction					
Parents					X
Adolescent					X

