### **Missing data, drop out and lost to follow up**

Loss to follow-up and missing data for various reasons is impossible to avoid in randomized trials. We will apply the analysis framework in which missing data related to the intention-to-treat approach depend on making plausible assumptions about the missingness of the data and including all participants in subsequent sensitivity analyses.

1. Attempt to follow up all randomized parents, even if they withdraw from allocated treatment.
2. Perform a main analysis of all observed data that are valid under a plausible assumption about the missingness of the data (i.e., Model-based: data as observed; using linear mixed effects models, assuming that data are 'Missing at Random' [MAR]).
3. Perform sensitivity analyses to explore the effect of departures from the assumption made in the main (#2) analysis (i.e., a non-responder-imputation: using the value at baseline to replace missing data will correspond to a non-responder imputation; these models will potentially be informative even if data are 'Missing Not At Random' [MNAR]).
4. Account for all randomized parents, at least in the sensitivity analyses (covered by #2 and #3 above, plus the corresponding analyses based on the per protocol population).

The interpretation of the corresponding statistical measures of uncertainty of the treatment effect and treatment comparisons will involve consideration of the potential contribution of bias to the P-value, 95% confidence interval, and of the inference in general.

Our primary analysis population will be all parents with available data at baseline, statistically modelled using repeated-measures linear mixed effects models (see above). These models will be valid if data are 'MAR'.

*Sensitivity:* We will analyze all variables, with missing data being handled by multiple imputation techniques.

When the different sensitivity analyses agree, and the analyses on the sensitivity analyses and the main analysis lead to essentially the same conclusions, confidence in the trial results is increased.

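### Randomisation does not wait for the parent's baseline readiness score, yet only parents who have one enter the primary analysis

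*Protocol*

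**What the plan says.** All references are to the Protocol.

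- **Randomisation:** "Randomisation will be conducted after screening and written consent of parents". The baseline questionnaire is not mentioned. The section goes on: "Those randomised to the intervention arm will then receive access to the intervention materials".
- **Data collection and management:** on the schedule, this section says "Data will be collected through questionnaires at baseline and every six months up to three months after the adolescent's transfer to adult care". On the mode: "Questionnaires will be sent out via email or by post based on participants' wishes". No order is given between return of the baseline form and allocation.
- **Abstract:** the trial is described "with main measurements at pre-intervention baseline, at transfer, and three months follow-up (post-intervention"). Baseline is thus placed before the intervention. It is not placed before randomisation.
- **Intervention:** the website is "available for parents from recruitment until follow-up".
- **Missing data, drop out and lost to follow up:** "Our primary analysis population will be all parents with available data at baseline", analysed with a repeated-measures linear mixed model under missing at random. The same section plans to try to follow up every randomised parent, and commits to accounting for all of them at minimum in the sensitivity analyses. Those are replacement of missing values by the baseline value, per-protocol analyses and multiple imputation.

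**The concern.** An analysis population defined by possession of a baseline value is harmless when that value is collected before allocation, because everyone randomised then has one. It is not harmless when the value can arrive, or fail to arrive, after allocation. Possession of a baseline is then a post-randomisation event.

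The arms are standard care and standard care plus a visible programme, so families know which they are in. A parent's willingness to return the first form may depend on that knowledge. If it does, the two arms of the primary analysis are no longer the two randomised groups, and the missing-at-random assumption does not help, since the model is fitted only to parents already admitted by the baseline rule.

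At stake is the randomised comparison of the primary outcome, in a trial planned at 31 families per arm with no allowance shown for loss.

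**Working it through.** **1. The order of events as the text leaves it.** The stated conditions for randomisation are screening and consent. Materials follow allocation. The form travels by email or post, so the site does not control its return date. The only statement on baseline timing, in the Abstract, is relative to the intervention. A parent could be randomised, learn the arm, and return the baseline form later or never, without any breach of the Randomisation section.

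**2. Who is lost, and whether the fallbacks recover them.**
- Primary mixed model: a parent without a baseline is outside the stated population, even with later TR scores.
- Baseline-value replacement: needs a baseline, so it cannot include this parent.
- Multiple imputation: can include this parent, but only as a sensitivity analysis.

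**3. The plan's own figure.** Inputs from Sample size: difference 0.50, SD 0.68, alpha 0.05 (two-sided assumed), power 0.80.
- Normal approximation: n = 2 × (1.96 + 0.84)² × (0.68/0.50)² ≈ 29.0, rounded up to 30 per group.
- Two-sample t-test: 30.03, rounded up to 31 per group, 62 in total. The stated figure is reproduced. Power at 31 per group is 0.813.

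**4. Illustration of size.** The Protocol gives no rate of missing baselines, so the following inputs are assumed: a fraction m of one arm is lost, and those lost differ by k SD from those kept. The mean of those kept then differs from the mean of the whole arm by m × k × 0.68.

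| m | k | Bias in unadjusted contrast (points) | Share of 0.50 |
|---|---|---|---|
| 10% | 0.25 | 0.10 × 0.25 × 0.68 = 0.017 | 3% |
| 10% | 0.5 | 0.10 × 0.5 × 0.68 = 0.034 | 7% |
| 20% | 0.25 | 0.20 × 0.25 × 0.68 = 0.034 | 7% |
| 20% | 0.5 | 0.20 × 0.5 × 0.68 = 0.068 | 14% |

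The sign depends on which arm loses parents and on whether they score low or high. Loss of low-scoring controls shrinks the estimated effect; loss of low-scoring intervention parents enlarges it.

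**5. Effect of baseline adjustment.** If those lost have the same deficit at baseline as at follow-up, and the baseline slope is b, the remaining bias is m × k × 0.68 × (1 − b). For an assumed b of 0.3 to 0.7, the range becomes 0.017 × 0.3 = 0.005 to 0.068 × 0.7 = 0.048 points. On change from baseline it is zero under this assumption.

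**6. Power with loss from one arm only (t-test).** 31 versus 27.9 (10% lost): 0.791. 31 versus 24.8 (20% lost): 0.764.

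**The case against.** The strongest reply is that the order is unstated rather than wrong. Randomising after consent is compatible with a baseline completed in between, and a figure in the Randomisation section is not shown in the text available and may depict the order. This stands as far as it goes: the Protocol does not say that baseline follows allocation. But no text read here makes it precede allocation either, and the exclusion rule in the missing-data section is explicit.

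A reader might go further and infer that intervention parents use the website before answering the baseline, since access is said to run from recruitment. The documents do not support that. The Randomisation section gives materials only after allocation and only to the intervention arm, so the phrase about recruitment is best read as loose wording, and the Abstract calls the baseline pre-intervention. What the Abstract does not exclude is knowledge of the allocation.

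A reader might also infer that disappointed controls are the likelier non-returners, or that the bias is a large part of the target. Nothing in the documents gives the direction, the rate or the difference in TR. A power of about 0.77 at 10% loss would need that loss in both arms, which is a different scenario from loss in one.

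The planned mitigation also deserves credit. Follow-up of all randomised parents is intended, multiple imputation can recover those without a baseline, and adjustment for baseline removes part of the bias. None of this changes the primary population.

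Finally, the matter cannot simply be left to the statistical analysis plan. Under Data analysis, that plan is to be written once every participant has finished the final measurement, when the order of baseline and allocation can no longer be changed.

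**Conclusion.** The point holds as a gap in trial conduct combined with a stated exclusion rule. The Protocol permits randomised parents to be left out of the primary analysis in a way that depends on known allocation, and only sensitivity analyses commit to all of them. It does not show that this has happened, or that any baseline was taken after exposure to the programme.

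The size is unknown. Under the assumed losses of 10-20% in one arm and differences of 0.25-0.5 SD, the unadjusted bias is about 0.02-0.07 points against a target of 0.50, in either direction and smaller after baseline adjustment. Power goes from 0.81 to about 0.79-0.76. These are modest amounts, but the change is cheap and protects the randomised comparison of the primary outcome, so it should be made.

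**What to change.** 1. **Randomisation section:** state that REDCap releases the allocation, and with it website access, only after the parent's baseline TR questionnaire is recorded. Request the adolescent's baseline at the same time, but do not let it block randomisation, because the primary outcome is the parent's score.
2. **Missing-data section:** define the primary population as all randomised parents. Model baseline as one of the repeated measures in the mixed model, so that a parent already randomised without a baseline still contributes any later TR scores.
3. **Families already enrolled** (the Trial status section says recruitment is ongoing): compare the date of baseline return with the date of allocation, and report by arm how many baselines are late or missing. This shows whether the problem has arisen.

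**Cost:** two sentences of text and a REDCap rule. Randomisation waits a short time, longer for postal forms. Families who never return the baseline are not randomised, which may slow recruitment towards 62 but leaves the comparison between arms intact.
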